## **6.2 Outcome Variables**

Feasibility is defined as participant retention (e.g., the number of participants that complete the intervention out of all participants randomized to an intervention arm), however others will be explored. Feasibility outcomes will be summarized using sample quantities and corresponding 80% confidence interval estimates. The intervention will be considered feasible if at least 80% of the participants randomized, complete the final follow-up.

Relevant inflammatory markers (C-reactive protein, interleukin-6, and brain derived neurotrophic factor) will be measured in blood collected from participants at baseline and final follow-up. Change in inflammatory markers will be calculated. The distribution of change in inflammatory markers will be summarized using sample quantities and kernel density estimates. We will develop 80% confidence interval estimates of inter- and intra-individual variation (i.e., standard deviation) of change in these measures.

Motivation to engage in physical activity will be assessed via self-report questionnaire, Motives for Physical Activities Measure-Revised. Change in motivation will be calculated between baseline and follow-up periods. The distribution of change in motivation scores will be summarized using sample quantities and kernel density estimates. We will develop 80% confidence interval estimates of inter- and intra-individual variation (i.e., standard deviation) of change in these measures.

Engagement in physical activity will be defined as the median daily-step count over 2 weeks prior to each mid-point and/or follow-up visit. We chose the median daily step count, because step counts varies from day to day. Change in median step count will be calculated between the baseline and follow-up. The distribution of change in physical activity will be summarized using sample quantities and kernel density estimates. We will develop 80% confidence interval estimates of inter- and intra-individual variation (i.e., standard deviation) of change in these measures.

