### 3.5 Study Endpoints

Primary Outcomes – The primary outcome for this study will be engagement in physical activity.

1. **Engagement in Physical Activity:** Engagement in physical activity will be evaluated by the median # of steps per/day (via ActiGraph) of the previous two weeks before each visit (e.g., 2 weeks before baseline or 2 weeks before follow-up). We will also evaluate median sedentary minutes/day of the previous two weeks before visits.

Secondary Outcomes – We will evaluate several secondary outcomes including:

1. **Feasibility** : Feasibility will be defined as participant retention rate (i.e., number of participants that complete the intervention/total randomized).
2. **Inflammatory Biomarkers:** Serum markers relevant to inflammation, (serum brain-derived neurotrophic factor, BDNF; C-reactive protein, CRP; interleukin-6, IL-6) at baseline and follow-up will be measured by Quest Diagnostics or our collaborators at the University of Connecticut Metabolic Phenotyping Lab.
3. **Motivation:** Motivation to engage in physical activity (our proposed mediator between inflammation and physical inactivity) will be assessed by the self-report questionnaire Motives for Physical Activities Measure-Revised that has been used in middle-aged and older adults.

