Visit 2, Week 4*:	
Assessments/Activities
 
 
1. Sync ActiGraph Data
 
2. Depression Level
 
3. Suicidal Ideation
 
4. Motivation
 
5. Symptoms
 
6. Compliance
 
 
Participants will be asked to:
 
 
1. Continue to wear an ActiGraph physical activity monitor
 
2. Avoid consumption of certain foods (e.g., blueberries that are rich in fiber and anthocyanins)
 
3. Fill out a 3-day dietary record in the week prior to next visit
 

Visit 3, Week 6:	
Assessments/Activities
 
 
1. Turn in Diet Records
 
2. Sync ActiGraph Data
 
3. Depression Level
 
4. Suicidal Ideation
 
5. Vitals
 
6. Weight
 
7. Blood Draw to Assess Serum Inflammatory Markers
 
8. Motivation
 
9. Social Network
 
10. Symptoms
 
11. Compliance
 
 
Participants will be asked to:
 
 
1. Continue to wear an ActiGraph physical activity monitor
 
2. Avoid consumption of certain foods (e.g., blueberries that are rich in fiber and anthocyanins)
 

Visit 4, Week 8*:	
Assessments/Activities
 
 
1. Sync ActiGraph Data
 
2. Depression Level
 
3. Suicidal Ideation
 

	
 
4. Motivation
 
5. Symptoms
 
6. Compliance
 
 
Participants will be asked to:
 
 
1. Continue to wear an ActiGraph physical activity monitor
 
2. Avoid consumption of certain foods (e.g., blueberries that are rich in fiber and anthocyanins)
 
3. Fill out a 3-day dietary record in the week prior to next visit
 

Visit 5, Week 12:	
Assessments/Activities:
 
 
1. Turn in Diet Records
 
2. Sync ActiGraph Data
 
3. Medical History and Health Behaviors
 
4. Vitals
 
5. Weight
 
6. Depression Level
 
7. Suicidal Ideation
 
8. Blood Draw to Assess Serum Inflammatory Markers
 
9. Motivation
 
10. Social Network
 
11. Symptoms
 
12. Compliance
 
13. Cognitive Status
 

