**3-Day Diet Records:** Diet records (consisting of 2 weekdays and 1 weekend day) will be reviewed by research staff for accuracy and completeness. Records will be entered into a dietary analysis program (e.g., Nutrition Data System for Research) to estimate dietary intake of nutrients.

**Height/Weight** will be measured at the baseline visit.

1. Height will be measured using a stadiometer.
2. Weight will be measured using a digital Health-o-meter scale.

**Vital Signs** (e.g., body temperature, pulse, and seated blood pressure) will be measured at the baseline visit. After 3-5 minutes of rest, seated blood pressure will be measured twice with an automated cuff.

**Motives for Physical Activities Measure-Revised (MPAM-R):** Motivation to engage in physical activity will be assessed with the MPAM-R, which is a self-report questionnaire has been used in middle-aged and older adults.

**Blood (up to 10 mL)** will be collected by a trained phlebotomist using sterile procedures. Blood will be processed and stored at -80 degree C for future analyses. Batch analyses of relevant inflammatory markers (e.g., C-reactive protein, interleukin-6, and brain-derived neurotrophic factor) will be measured by a reputable lab (e.g., Quest or collaborators at the University of Connecticut).

**Relevant Symptoms:** Information on relevant symptoms including gastrointestinal distress, appetite, pain etc., will be collected by self-report.

**Compliance:** Compliance with our dietary intervention will be evaluated throughout the study. Participants will be asked to log consumption of their powder and keep all of their used powder packets. At the study visit, participants will return all unused and used powder packets to estimate number of intended doses that were consumed.

**Week 4 Mid-point Visit (~45 minutes):** The Week 4 Mid-point Visit will include an evaluation of motivation, depression level (PHQ-9), suicidal ideation, relevant symptoms and compliance. Participants will again be asked to continue to wear the ActiGraph and provided with new 3-day diet records to fill out the week prior to their next visit.

**Week 6 Mid-point Visit (~45 minutes):** The Week-6 Mid-point Visit will be the same as Week 4 Mid-point Visit, but it will also include turning in diet records, a blood draw of ~10 mL, as well as an evaluation of vitals and social network.

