### 5.4 Outcome Measures

Our primary endpoint is engagement in physical activity after 12 weeks of the dietary intervention. Secondary outcomes include feasibility, inflammatory markers, and motivation; however, we will also explore alternative outcomes.

Name	Type	Timeframe	Brief description
Feasibility	Secondary	Throughout the entire study	Participant retention (e.g., the number of participants that complete the intervention out of all participants randomized to an intervention arm)
Inflammatory Markers	Secondary	Baseline, Week 6, and Final Follow-up (Week 12)	C-reactive protein, interleukin-6, and brain derived neurotrophic factor will be measures in blood collected from participants.
Motivation	Secondary	Baseline, Week 4, Week 6, Week 8, and Final Follow-up (Week 12)	Motivation to engage in physical activity will be assessed via self-report questionnaire, Motives for Physical Activities Measure-Revised,
Engagement in Physical Activity	Primary	Baseline, Week 4, Week 6, Week 8, and Final Follow-up (Week 12)	Median daily-step count over the 2 previous weeks.

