## **6.3 Statistical Methods**

Formal inference and estimation of treatment effects will use a Student's t-test. The mean change (baseline-follow-up) in our outcome variables (inflammatory markers, motivation, step count) in the control group will be compared to the mean change (baseline-follow-up) of the intervention group overtime. A p-value less than 0.05 will be used to determine statistical significance.

The relationship between inflammatory markers, motivation, and engagement in physical activity will be assessed. Given that consistent evidence in populations (including older adults) have shown that supplementation with berries (a source of fiber and anthocyanins) successfully reduces inflammatory markers, we are confident our intervention will successfully lower inflammatory markers. Thus, we will evaluate the relationship between of change in inflammatory markers with change of physical activity utilizing a linear regression.

To determine if change in motivation is on the pathway between change in inflammation and engagement in physical activity, we will use linear regression with and without the addition of change in motivation to the model. If adjusting for change in motivation changes the estimate by >10%, then motivation will be considered a part of the causal pathway. A p-value less than 0.05 will be used to determine statistical significance.

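### Week 6 is a scheduled inflammatory-marker timepoint with no stated analysis, and the change-score t-test drops anyone who has Week 6 but not Week 12 blood

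*Combined protocol and SAP*

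**What the plan says.** **Where Week 6 is a marker timepoint.** The outcome table in Section 5.4 gives the marker timeframe as "Baseline, Week 6, and Final Follow-up (Week 12". The Week 6 visit in the Section 5.1 schedule includes "Blood Draw to Assess Serum Inflammatory Markers", and Table 1 marks serum markers at 6 weeks. The Week 6 visit description in Section 5.2 says "it will also include turning in diet records, a blood draw of ~10 mL".

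**Where it is not.** Section 3.5 describes serum markers "at baseline and follow-up will be measured by Quest Diagnostics" or a collaborating laboratory. Section 6.2 says the markers "will be measured in blood collected from participants at baseline and final follow-up", after which a change is calculated.

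**What is analysed.** Section 6.3 uses a Student's t-test on "The mean change (baseline-follow-up) in our outcome variables (inflammatory markers, motivation, step count) in the control group" against the same quantity in the intervention group. It also relates "change in inflammatory markers with change of physical activity utilizing a linear regression". Section 6.2 promises "80% confidence interval estimates of inter- and intra-individual variation (i.e., standard deviation) of change in these measures". Chapter 6 never names Week 6 and contains no repeated-measures model. Section 6.1 applies intent to treat to all analyses; Chapter 6 gives no method for missing data.

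**The concern.** The sections that schedule the markers and the sections that define and analyse them disagree on how many timepoints there are. With 40 participants and three draws each, 120 marker samples are planned before attrition, and 40 of them (one third) have no stated role in the analysis.

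Three things follow.

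- **Lost participants.** A change score from baseline to final follow-up needs Week 12 blood. Someone who gives blood at Week 6 and then leaves contributes nothing to the Aim 2 comparison, although the plan states intent to treat and Section 4.4 keeps data collected before withdrawal.
- **An output that the named data cannot produce.** Section 6.2 wants both inter- and intra-individual variation of change, and two measurements give each person only one change.
- **Room for choice after the fact.** While 5.4 and 6.2 disagree, Week 6 results for three markers could be reported or left out once the data are seen.

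**Working it through.** The plan gives no power or precision figure for the markers, so there is nothing of its own to reproduce. The check has three parts.

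**1. Timepoints side by side**

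| Section | Marker timepoints |
|---|---|
| 3.5 Study Endpoints | baseline, follow-up |
| 5.1 visit schedule, 5.2 visit text, Table 1 | baseline, Week 6, Week 12 |
| 5.4 Outcome Measures | baseline, Week 6, Week 12 |
| 6.2 Outcome Variables | baseline, final follow-up |
| 6.3 Statistical Methods | one change, baseline to follow-up |

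**2. Intra-individual SD of change**

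Baseline and Week 12 yield one change per person. The spread of those changes across people mixes true between-person differences with within-person fluctuation, and one value per person cannot separate them. Week 6 is the only other scheduled marker measurement that could.

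**3. Size of the effect on the Week 12 comparison**

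Inputs:

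- 20 per arm (Section 6.4).
- Assumed: 20% of each arm (4 people) lost, all after Week 6, so 20 per arm at Week 6 and 16 at Week 12. The 20% matches the non-completion that the 80% feasibility threshold in 6.2 would tolerate; the timing is an assumption.
- Assumed: equal variance σ² and equal correlation ρ between any two visits, with ρ from 0.5 to 0.8. The documents give no correlation.
- Large-sample variances, so the small cost of estimating the extra parameters is ignored.

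Step a, change score. The variance per person is 2(1−ρ)σ².

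Step b, Week 12 adjusted for baseline, same completers. The variance per person is (1−ρ²)σ². The ratio to step a is (1−ρ²)/[2(1−ρ)] = (1+ρ)/2:

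- ρ = 0.5: 0.75, a fall of 25%
- ρ = 0.8: 0.90, a fall of 10%

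No Week 6 data are involved so far.

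Step c, add Week 6. Given baseline, the correlation of Week 6 with Week 12 is r = (ρ−ρ²)/(1−ρ²) = ρ/(1+ρ), which is 0.333 at ρ = 0.5 and 0.444 at ρ = 0.8. Using all 20 Week 6 values, the Week 12 variance relative to step b is 1 − r²(1 − 16/20) = 1 − 0.2r²:

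- ρ = 0.5: 1 − 0.2 × 0.111 = 0.978
- ρ = 0.8: 1 − 0.2 × 0.198 = 0.960

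Step d, combined ratio to the change score:

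- ρ = 0.5: 0.75 × 0.978 = 0.73, a fall of 27%
- ρ = 0.8: 0.90 × 0.960 = 0.86, a fall of 14%

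Sensitivity to timing. If half of the loss comes before Week 6 (18 per arm at Week 6, 16 at Week 12), the factor in step c becomes 1 − r²(1 − 16/18) = 1 − 0.111r², or 0.988 to 0.978. The Week 6 contribution is then about 1-2% of the variance.

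**The case against.** **Nothing says that Week 6 is thrown away.** A reader might infer that the blood is collected and then discarded. The documents do not support that. Section 6.3 speaks of change over time and leaves follow-up undefined, the intra-individual variation in 6.2 may tacitly rely on Week 6, and Section 5.2 has the blood stored frozen for batch assay. What stands is narrower: no Week 6 analysis is stated. Since 6.2 describes when the markers are measured, even the Week 6 assay is in doubt.

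**The planned contrast answers Aim 2.** Aim 2 asks about change after 3 months, which baseline to Week 12 addresses directly. A mid-point sample may properly be descriptive, and the Week 12 comparison can be run without it. This stands, and it is why Week 12 should remain the main contrast. It does not answer the loss of participants with Week 6 blood only.

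**The gain is mostly not about Week 6.** This is right. It would be wrong to credit the full 14-27% to the extra draw; baseline adjustment supplies nearly all of it. The 2-4% from Week 6 is the favourable case, about 1-2% of the standard error (√0.978 = 0.989, √0.960 = 0.980), and estimating extra parameters in a trial this small would take some of it back.

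**Averaging Weeks 6 and 12 would look far more precise.** It would, but the average is a different estimand from Aim 2's 3-month effect, and the plan does not say that the two effects are equal. That gain is not counted here.

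**Markers are a minor place to raise this.** They are secondary outcomes in a pilot sized on step count, and 5.4 lists interim timepoints for motivation and step count that 6.3 also reduces to one change. That limits the severity but does not remove the inconsistency.

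**Conclusion.** The point holds as an inconsistency with a modest statistical cost, and it should be corrected. Sections 3.5 and 6.2 disagree with 5.1, 5.2, Table 1 and 5.4 on whether Week 6 is a marker timepoint. No Week 6 marker analysis is stated. The t-test in 6.3 loses anyone without Week 12 blood, and the two timepoints named in 6.2 cannot give the intra-individual SD that the same section promises. These conclusions rest on the text alone.

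The precision figures rest on assumed equal correlations of 0.5-0.8 and an assumed 20% loss after Week 6. They show a fall of about 14-27% in the variance of the Week 12 arm difference from changing the analysis, of which the Week 6 data are a small part. The stronger case for using Week 6 is that it keeps participants who leave after that visit, makes within-person variability estimable, and settles before the data are seen what will be reported. None of this makes the Week 12 comparison invalid.

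**What to change.** 1. In Sections 3.5 and 6.2, name the marker timepoints as baseline, Week 6 and Week 12, to agree with 5.4.
2. In Section 6.3, replace the change-score t-test for the markers with a repeated-measures mixed model of the Week 6 and Week 12 values. Include arm, visit, arm-by-visit and the baseline value, on the log scale if a marker is skewed (6.1 already allows transformation). State that the Week 12 contrast is the main result and the Week 6 contrast is supportive. People lost before Week 6 have no post-baseline value and still do not contribute.
3. In Section 6.2, say that the intra-individual variation of the markers is estimated from all three timepoints.
4. Check the interim step-count and motivation timepoints in 5.4 against 6.3 in the same way.

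Cost: SAP wording and a few lines of code. The draw is already scheduled and 5.4 already lists the Week 6 measurement. Assay cost is new only if 6.2 was meant to say that Week 6 blood is not assayed; it would then be at most 40 samples × 3 markers = 120 additional assays.

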**Week 8 Mid-point Visit (~45 minutes):** The Week-8 Mid-point Visit will be the same as Week 4 Mid-point Visit.

**Week 12 Final Follow-up Visit (~60 minutes):** At the final follow-up visit, participants will be asked to turn in their 3-day diet records and synchronize their ActiGraph devices to transfer their activity data and evaluate engagement in physical activity. Medical history/health behaviors, weight, suicidal ideation (P4SS), social network, depression level (PHQ-9), motivation, vitals, cognitive status (MoCA) and relevant symptoms will be evaluated. Additionally, up to 10 mL of blood will be taken to measure inflammation-related markers in serum. Dietary compliance will also be estimated as previously described.

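### The Aim 3 mediation analysis uses essentially concurrent changes, so it cannot tell motivation driving steps from steps driving motivation, yet section 6.3 would declare a causal pathway

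*Combined protocol and SAP*

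**What the plan says.** Section 3.5 calls motivation the proposed mediator between inflammation and inactivity. Aim 3 in section 3.1 expects much of the effect on steps to pass through it.

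- **Steps.** Section 6.2 uses the "median daily-step count over 2 weeks prior to each mid-point and/or follow-up visit". Sections 3.5 and 5.4 give the same backward-looking window.
- **Motivation.** The questionnaire (MPAM-R) is given at the visits, including Week 12 (section 5.1, Table 1 and the Week 12 description in 5.2). Section 6.2 says: "Change in motivation will be calculated between baseline and follow-up periods".
- **Markers.** At Week 12, "up to 10 mL of blood will be taken to measure inflammation-related markers in serum". For analysis, section 6.2 says the markers "will be measured in blood collected from participants at baseline and final follow-up".
- **Decision.** Section 6.3 regresses step change on marker change, with and without motivation change: "If adjusting for change in motivation changes the estimate by >10%, then motivation will be considered a part of the causal pathway".

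Section 5.4 and Table 1 also schedule blood at Week 6, and motivation and steps at Weeks 4, 6 and 8. Section 6.3 describes no lagged or reverse-direction analysis.

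**The concern.** The hypothesis has an order: inflammation, then motivation, then activity. The analysis variables do not. Steps summarise the 14 days that end at the Week 12 visit, and motivation and blood are taken when those days end. If people who walk more come to report stronger motives for activity, motivation change will correlate with step change, and adjusting for it will shrink the marker coefficient just as mediation would.

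A route for this exists in the protocol. At baseline every participant is given a daily step goal 20% above their own median and encouraged to meet it (section 5.2, Baseline Visit). Both arms receive the goal, so the association could arise with no supplement effect.

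What is at stake is the wording of the Aim 3 conclusion. Section 8.6 says later trials will build on this pilot, and a pathway claim that the data cannot support would carry forward.

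**Working it through.** **1. Time order at the final visit.** The step window is Weeks 10–12; motivation and blood are taken at Week 12. The window's midpoint precedes the visit by 14/2 = 7 days. Against changes accrued over 12 weeks, that is essentially concurrent.

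**2. Inputs.** The plan gives no figure for mediation to reproduce. The sample size of 40 (20 per group) is from section 6.4. The documents give no correlation among markers, motivation and steps, so all correlations below are assumed.

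**3. Expected shift with no mediation.** Let marker change X relate to step change Y with correlation a, let Y drive motivation change M with correlation r, and let M have no effect on Y. In standardised units the unadjusted coefficient is a, and the coefficient adjusted for M is a(1 − r²)/(1 − a²r²). The proportional shift is therefore

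r²(1 − a²)/(1 − a²r²).

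With a = 0.3:

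| r | Calculation | Shift |
|---|---|---|
| 0.30 | 0.0819/0.9919 | 8% |
| 0.33 | 0.0991/0.9902 | 10% |
| 0.40 | 0.1456/0.9856 | 15% |
| 0.50 | 0.2275/0.9775 | 23% |
| 0.60 | 0.3276/0.9676 | 34% |

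The 10% line is crossed at r of about 0.33.

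**4. How often the rule fires at n = 40.** Simulating the same model with a = 0.3, the rule (a shift above 10% in either direction) declares motivation on the pathway in about 52% of trials at r = 0.3, 68% at 0.4 and 81% at 0.5. Separate runs spanned 52–82%. The motivation coefficient has p<0.05 in about 45–90% of trials over the same range. With n = 36 the firing rates are similar (54%, 68%, 80%).

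**5. How much is the rule itself.** If M is pure noise, the rule still fires in 22% of trials at a = 0.3, and in 7–34% as a runs from 0.5 down to 0.2. Part of the rate in step 4 therefore belongs to the 10% threshold. The p-value result in step 4 does not depend on that threshold.

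**6. What time ordering does under the reverse model.** Take Week 8 motivation and Weeks 10–12 steps, with a correlation of about 0.73 between step measures at Weeks 8 and 12. Without adjustment for Weeks 6–8 steps, the 10% rule still fires in 40–69% of trials. With that adjustment, the motivation coefficient has p<0.05 in 4–5%, the nominal rate.

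**7. What time ordering does if mediation is real.** Suppose motivation acts on steps in the same period: marker–motivation correlation 0.5, motivation–steps 0.4–0.6, motivation stability between Weeks 8 and 12 of 0.6–0.8, and step-residual correlation 0.73. The lagged model adjusted for Weeks 6–8 steps then reaches p<0.05 in only about 5–16% of trials, against 61–96% for the concurrent motivation coefficient. The earlier steps already carry motivation's effect, so adjusting for them removes it. If the effect is truly delayed, the figure is 32–93%.

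**The case against.** The strongest reply is that a 7-day offset hardly amounts to measuring the mediator after the outcome. The documents give no recall period for the questionnaire, so a Week 12 score may well reflect motivation during the step window. This stands. A reader might infer that the mediator is measured in the wrong order and that reverse causation is likely; the documents support neither. They show concurrent measurement and make reverse causation possible. The step goal supplies a route, but nothing in the documents shows that walking raises questionnaire scores.

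It is also fair that every magnitude above is assumed, that the 10% rule would be too loose with perfect timing, and that this is a 40-person pilot seeking preliminary evidence, with mediation not its primary endpoint. The plural follow-up periods in section 6.2 might admit earlier motivation scores, but no text pairs an earlier score with a later step window.

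A reader might also infer that the lagged model should replace the planned one as the main Aim 3 evidence. Step 7 of the working argues against that, because the lagged model could easily miss real same-period mediation.

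None of this rescues the causal-pathway declaration, which is the part of the plan at issue.

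**Conclusion.** The concern holds in a limited form. The planned regression compares concurrent changes and cannot identify direction, so section 6.3's conclusion goes further than its data allow. Under a pure reverse model with marker–step correlation 0.3, a steps–motivation correlation of about 0.33 is enough for the expected shift to exceed 10%, and at n=40 the false-declaration rate is about 52–82% for correlations of 0.3–0.5. These sizes rest on assumed correlations and include the contribution of the loose threshold. The limit on interpretation does not depend on them.

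The marker is affected too. In section 6.3 it is the exposure, and its follow-up sample is also drawn as the step window closes, so the marker–step link could run backwards as well. Adding a treatment-arm term would not cure the timing.

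**What to change.** In section 6.3, describe the Week 12 result as an association consistent with mediation, and do not conclude from it alone that motivation is part of the causal pathway.

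Pre-specify two exploratory sensitivity analyses:

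- **Time-ordered model:** marker change to Week 6, motivation change to Week 8, and steps in Weeks 10–12, with baseline values as covariates. Fit it with and without Weeks 6–8 steps and report both, since the first guards against reverse causation and the second keeps more of any same-period effect.
- **Reverse model:** Weeks 6–8 steps predicting Week 12 motivation.

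State beside them that the model adjusted for earlier steps may have only about 5–16% power at n=40 under the assumed same-period inputs, so a null result must not be read as evidence against mediation. These models improve the evidence on direction but do not prove causation.

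The cost is SAP wording and a few regressions, with no new visit or measurement. One practical point needs settling. Section 5.1 waives the ActiGraph sync for some phone visits. Its asterisks mark Weeks 4 and 8, while the footnote names visits 3 and 5, so the two should be reconciled. If the Week 8 visit is by phone, the Weeks 6–8 step data must be retrieved at a later sync.
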